GB-102 is lyophilized and reconstituted with hyaluronic acid prior to intravitreal administration to produce an administered IVT dose of 1 mg or 2 mg sunitinib in a 50 µL injection using a 27-gauge needle. Subjects will receive their assigned dose (1 mg or 2 mg GB-102) on Day 1 as a single IVT injection.

**Reference Therapy,
Dose, and Mode of
Administration:**

No reference therapy is provided in this study (ie, there is no active control arm)

Study Endpoints:

Primary Safety Endpoint

- Occurrence of ocular and non-ocular adverse events and serious adverse events at all study visits

Secondary Pharmacodynamic Endpoints

- BCVA (ETDRS protocol) at all study visits
- CST (SD-OCT) at all study visits
- Observed subjects rescue-free at each study visit

Statistical Methods:

Analysis Population

- **Safety analysis set (SS):** Includes all subjects who receive a dose of study treatment. Subjects who receive rescue treatment during the study will be included in the SS. Subjects will be analyzed according to actual treatment received.
- **Full analysis set (FAS):** Includes all subjects who receive a dose of study treatment, and complete the baseline and at least one post-baseline visit. All data collected from subjects who receive rescue treatment during the study will be included in the FAS. Subjects will be analyzed according to their assigned treatment regardless of actual treatment received.
- **Per protocol analysis set (PP):** Consists of a subset of the FAS and includes subjects with no major protocol violations that would affect the assessment of the pharmacodynamics and rescue data. Data collected after the receipt of rescue therapy during the study will not be included in PP analyses.

Safety Endpoint Analyses

All reported adverse events will be coded using the Medical Dictionary for Regulatory Activities (MedDRA). Treatment-emergent adverse events (TEAEs) will be summarized by system organ class (SOC) and preferred term (PT). Frequencies and percentages will be provided by treatment group for subjects with TEAEs, treatment related TEAEs, serious TEAEs, serious treatment related TEAEs, TEAEs leading to premature study discontinuation and TEAEs by maximum severity. Separate analyses will be performed for ocular AEs in the study eye, ocular AEs in the non-study eye, and nonocular AEs.

The SS will be the primary population used for analysis of the primary safety endpoint.

Pharmacodynamic Endpoint Analyses

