9.2.2 Secondary Pharmacodynamic Endpoints

- BCVA at all study visits
- CST at all study visits
- Observed subjects who are rescue-free at each study visit

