### **12. Pharmacodynamic Analysis**

BCVA, CST (using SD-OCT), and rescue treatment (time to first rescue treatment, number of rescue treatments) will be included as pharmacodynamic endpoints. No formal hypothesis testing will be conducted. Descriptive summaries will include the arithmetic mean, SD, median, minimum, and maximum values for continuous variable, and the number of subjects and percentages for categorical variable.

Observed data will contain assessments performed during protocol defined and unscheduled visits including ones performed after the first rescue treatment. To allow for an efficacy assessment of GB-102 while excluding potential effects from rescue injections data collected after first rescue treatment will be censored and replaced with the last value collected prior to the first rescue treatment. The LOCF approach is used for the analysis of BCVA and CST.

Sensitivity analysis will also be conducted using observed data without any censoring and imputation as mentioned in the previous paragraph.

The response to anti-VEGF rescue treatment is assessed for BCVA and CST based on the data collected prior and after the first rescue treatment. This response analysis will include all subjects receiving at least one rescue treatment. The last assessment performed before receiving the first rescue treatment will be used as the rescue treatment related baseline value. Data from one month and two months prior to the rescue treatment - baseline as well as one and two months post rescue treatment will be used to assess

the response to rescue treatment. These five timepoints will represent the time-scale for these analyses. No imputation for missing data will be done.

Summaries will be produced for the overall as well as by diagnosis (DME or RVO) within FAS and PP analysis set.

All observed pharmacodynamic variables will also be presented by visit in subject listings.

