### 12.3 Rescue-free treatment

Rescue treatment (any anti-VEGF agent; afibercept, bevacizumab, or ranibizumab) for all subjects enrolled is allowed at any visit following the Day 30 study assessments in subjects who meet any of the following criteria regarding decrease in BCVA and/or increase in CST:

Decrease in BCVA:

- $\geq 10$  ETDRS letter decrease compared with best on-study (i.e., post-treatment) BCVA ETDRS letter score

Increase in CST (any of the following criteria)

- $\geq 75$   $\mu\text{m}$  compared with the average of the last 2 on-study (i.e., post-treatment) visit CST measurements ( $\mu\text{m}$ ), and/or,
- $\geq 100$   $\mu\text{m}$  compared with the lowest on-study (i.e., post-treatment) CST measurement ( $\mu\text{m}$ )

Subjects may receive rescue treatment during a scheduled or unscheduled visit. Rescue treatment received during an unscheduled visit will be counted towards next scheduled visit.

Time to first rescue treatment including median time to first rescue treatment will be assessed using Kaplan-Meier product-limit approach by cohort. Subjects will be considered to have an event at the date where rescue treatment for study eye was first initiated. Since rescue treatment may be initiated at any time – at a scheduled visit or between scheduled visits – the timing of rescue treatment usage will be based on the date in at which rescue treatment was started. Subjects who do not have any usage of rescue treatment in the study eye will be censored at the date of the last visit. Subjects who discontinue prior to completing all treatment period visits will be evaluated based on the visits which are available. Kaplan-Meier plots will be generated.

For the subgroup of subjects with rescue treatment the time to first rescue treatment will be summarized by cohort using continuous descriptive statistics.

Proportion of subjects receiving rescue treatment during any protocol defined visit will be tabulated by cohort. As subjects will be eligible to receive rescue treatment on or after Day 30, Month 1 will be the first visit to be included in this table.

A contingency table will be generated to represent a cross-classification between whether rescue criteria were met (yes or no) versus received rescue treatment (yes or no). Contingency will be checked across all visits as well as at every visit starting from Month 1.

The total number of rescue treatments received by each subject will be tabulated.

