| Table 14.2.2.8        | Change from Baseline in Retinal CST (Using SD-OCT in $\mu\text{m}$ ) in the Study Eye at Scheduled Visits by Diagnosis     | Per Protocol Analysis Set – LOCF With Censoring For Rescue  |
| Table 14.2.3.1 | Time to Receipt of Rescue Treatment Using Kaplan-Meier Approach   | Full Analysis Set  |
| Table 14.2.3.2        | Time to Receipt of Rescue Treatment Using Kaplan-Meier Approach  | Per Protocol Analysis Set   |
| Table 14.2.3.3        | Time to Receipt of Rescue Treatment Using Kaplan-Meier Approach by Diagnosis   | Full Analysis Set   |
| Table 14.2.3.4        | Time to Receipt of Rescue Treatment Using Kaplan-Meier Approach by Diagnosis   | Per Protocol Analysis Set   |

|                       |  |                           |
|-----------------------|--|---------------------------|
| Table 14.2.3.5        | Mean Time to Receipt of First Rescue Treatment Among Rescued Subjects  | Full Analysis Set         |
| Table 14.2.3.6        | Mean Time to Receipt of First Rescue Treatment Among Rescued Subjects  | Per Protocol Analysis Set |
| Table 14.2.3.7        | Mean Time to Receipt of First Rescue Treatment Among Rescued Subjects by Diagnosis   | Full Analysis Set         |
| Table 14.2.3.8        | Mean Time to Receipt of First Rescue Treatment Among Rescued Subjects by Diagnosis   | Per Protocol Analysis Set |
| Table 14.2.4.1 | Proportion of Subjects Receiving Rescue Treatment by Visit  | Full Analysis Set  |
| Table 14.2.4.2        | Proportion of Subjects Receiving Rescue Treatment by Visit   | Per Protocol Analysis Set |
| Table 14.2.4.3        | Proportion of Subjects Receiving Rescue Treatment by Visit, and Diagnosis  | Full Analysis Set         |
| Table 14.2.4.4        | Proportion of Subjects Receiving Rescue Treatment by Visit, and Diagnosis  | Per Protocol Analysis Set |
| Table 14.2.4.5        | Contingency Table Showing Proportion of Subjects Receiving Rescue Treatment and Meeting Treatment Criteria by Visit                | Full Analysis Set         |
| Table 14.2.4.6        | Contingency Table Showing Proportion of Subjects Receiving Rescue Treatment and Meeting Treatment Criteria by Visit                | Per Protocol Analysis Set |
| Table 14.2.4.7        | Contingency Table Showing Proportion of Subjects Receiving Rescue Treatment and Meeting Treatment Criteria by Visit, and Diagnosis | Full Analysis Set         |

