| Table 14.2.4.8        | Contingency Table Showing Proportion of Subjects Receiving Rescue Treatment and Meeting Treatment Criteria by Visit, and Diagnosis | Per Protocol Analysis Set |
| Table 14.2.5.1        | Total Number of Rescue Treatments Received by Each Subject   | Full Analysis Set         |
| Table 14.2.5.2        | Total Number of Rescue Treatments Received by Each Subject   | Per Protocol Analysis Set |
| Table 14.2.5.3        | Total Number of Rescue Treatments Received by Each Subject, and Diagnosis  | Full Analysis Set         |
| Table 14.2.5.4        | Total Number of Rescue Treatments Received by Each Subject, and Diagnosis  | Per Protocol Analysis Set |
| Table 14.2.6.1        | Time in the Study From First Rescue Treatment Received by Each Subject   | Full Analysis Set         |

|                       |  |   |
|-----------------------|--|---|
| Table 14.2.6.2        | Time in the Study From First Rescue Treatment Received by Each Subject   | Per Protocol Analysis Set                                       |
| Table 14.2.6.3        | Time in the Study From First Rescue Treatment Received by Each Subject, and Diagnosis  | Full Analysis Set   |
| Table 14.2.6.4        | Time in the Study From First Rescue Treatment Received by Each Subject, and Diagnosis  | Per Protocol Analysis Set                                       |
| Table 14.2.8.1        | Change in Number of Letters Read Correctly (Using BCVA) in Response to Anti-VEGF Rescue Treatment at Scheduled Visits in the Study Eye               | Full Analysis Set with a Rescue Treatment – As Observed         |
| Table 14.2.8.2        | Change in Number of Letters Read Correctly (Using BCVA) in Response to Anti-VEGF Rescue Treatment at Scheduled Visits in the Study Eye               | Per Protocol Analysis Set with a Rescue Treatment – As Observed |
| Table 14.2.8.3        | Change in Number of Letters Read Correctly (Using BCVA) in Response to Anti-VEGF Rescue Treatment at Scheduled Visits in the Study Eye, by Diagnosis | Full Analysis Set with a Rescue Treatment – As Observed         |
| Table 14.2.8.4        | Change in Number of Letters Read Correctly (Using BCVA) in Response to Anti-VEGF Rescue Treatment at Scheduled Visits in the Study Eye by Diagnosis  | Per Protocol Analysis Set with a Rescue Treatment – As Observed |

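### The secondary endpoint of being rescue-free at each visit is left undefined and has no table of its own, and the by-visit criteria-met table can pair a rescue with measurements taken after it

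*SAP*

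**What the plan says.** The protocol synopsis lists the endpoint as "Observed subjects rescue-free at each study visit", and section 9.2.2 has "Observed subjects who are rescue-free at each study visit". SAP section 3 repeats it and lists time to first rescue as a separate item. SAP section 12 then names the rescue endpoints differently: "rescue treatment (time to first rescue treatment, number of rescue treatments) will be included as pharmacodynamic endpoints".

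SAP 12.3 has rescue-free in its heading but does not define it. It plans:

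- a survival analysis: "Time to first rescue treatment including median time to first rescue treatment will be assessed using Kaplan-Meier product-limit approach by cohort" (Tables 14.2.3.1 to 14.2.3.4, with three figures in section 17);
- receipt by visit from Month 1: "Proportion of subjects receiving rescue treatment during any protocol defined visit will be tabulated by cohort", under the title "Proportion of Subjects Receiving Rescue Treatment by Visit" (Tables 14.2.4.1 to 14.2.4.4, the first of them topline);
- "Contingency Table Showing Proportion of Subjects Receiving Rescue Treatment and Meeting Treatment Criteria by Visit" (Tables 14.2.4.5 to 14.2.4.8 with the versions by diagnosis), checked at each visit from Month 1 and over all visits;
- "Total Number of Rescue Treatments Received by Each Subject" (Tables 14.2.5.1 to 14.2.5.4), and a listing of rescues by subject.

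SAP 12.3 assigns a rescue given at an unscheduled visit to the scheduled visit that follows. For subjects who leave early it says only that their available visits are used.

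**The concern.** GB-102 is meant to reduce injection frequency (Protocol 1.3), so the share of eyes still without rescue at each visit is a natural durability figure, and the plan lists it as an endpoint. A count of who received rescue at a visit is a different quantity. A subject rescued once at Month 2 is absent from the Month 3 receipt count, yet is no longer rescue-free if the status is cumulative. Without a definition and a denominator, two programmers could report different results from the same data, and in an open-label study the choice could be made with the data in view.

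The second issue concerns the contingency tables. They are there to show whether rescue followed the criteria. If a rescue is moved to a later visit and judged on that visit's BCVA and CST, an eye that improved after the injection can appear as rescued without meeting the criteria.

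**Working it through.** The plan gives no figure on this point to reproduce. The check uses counts alone.

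**Inputs.** Ten subjects per dose (SAP 4.1). Six visits, Months 1 to 6 (SAP 12.3 and Table 1 in SAP 4.2). Rescued subjects stay in follow-up (protocol synopsis, rescue criteria). Repeat rescue is possible, since totals per subject are tabulated (SAP 12.3). Usual anti-VEGF interval 4 to 8 weeks (Protocol 1.3). Windows of ±7 days from Month 2 on. The rescue patterns below are assumptions chosen for illustration.

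**1. Receipt against cumulative status.** Receipt at visit k is the number rescued at k, divided by 10. Cumulative rescue-free status at k is (10 − distinct subjects rescued by k) / 10. Take no dropout and a receipt row of 1/10 at every visit:

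| Who is rescued | Rescue-free, Month 3 | Rescue-free, Month 6 |
|---|---|---|
| a new subject each time | 7/10 = 70% | 4/10 = 40% |
| two subjects, alternating | 8/10 = 80% | 8/10 = 80% |
| one subject every month | 9/10 = 90% | 9/10 = 90% |

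If nobody is re-treated at consecutive visits, the Month 6 range is 40% to 80%. With 2/10 at every visit, the extremes at Month 6 are 80% (the same two subjects) and 0% (all ten reached by Month 5). On a visit-specific reading the answer is simply the complement, 9/10 = 90% at every visit in the table above.

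**2. What the other outputs add.** Tables 14.2.5.1 to 14.2.5.4 separate the three patterns at study end: six subjects with one rescue, two with three, or one with six. They do not do so by visit. Without dropout the Kaplan-Meier estimate equals the cumulative proportion. For the first pattern it is 9/10 × 8/9 × 7/8 × 6/7 × 5/6 × 4/5 = 4/10 after the sixth rescue.

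**3. Denominator.**

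- Six of 10 rescued, two of those six later withdrawn: 4/8 = 50% rescue-free among those still in the study, 4/10 = 40% if all rescued subjects stay in.
- Four of 10 rescued, two others leave unrescued: 4/8 = 50% without the two, 6/10 = 60% if they are kept as rescue-free. Kaplan-Meier depends on when they leave. With rescues on Days 60, 90, 120 and 150:
  - leaving on Days 14 and 30: 7/8 × 6/7 × 5/6 × 4/5 = 0.500;
  - leaving on Days 61 and 91: 9/10 × 7/8 × 5/6 × 4/5 = 0.525;
  - leaving on Days 121 and 151: 9/10 × 8/9 × 7/8 × 5/6 = 0.583.

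**4. Final Kaplan-Meier time point.** Day 173 (180 − 7) is a tempting last time point because completers are censored from then on. It misses rescues given at a later Month 6 visit. In the first pattern on nominal days, five rescues fall by Day 150 and one on Day 180. The Day 173 estimate is 5/10 = 50%, while the count through the Month 6 visit is 4/10 = 40%.

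**5. Pairing in the contingency tables.** Longest gap: Month 2 visit on Day 53 (60 − 7), unscheduled rescue on Day 54, Month 3 visit on Day 97 (90 + 7), so 97 − 54 = 43 days. Shortest: rescue on the day before the scheduled visit, 1 day. Both assume that the next visit is attended.

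**The case against.** The strongest reply is that the planned package already shows durability. The Kaplan-Meier tables and plots, overall and by diagnosis, give the cumulative rescue-free probability over time, and Table 14.2.3.1 is topline. The rescue-count tables resolve the Month 6 example, so the 40% to 90% range exists only if the receipt row is read alone. This stands. A reader might infer that the rescue-free share cannot be recovered from the planned output, and the documents do not support that. Nor does receipt fail on every reading: if the endpoint means no rescue at that visit, the complement gives it once a denominator is stated.

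A reader might also argue that Kaplan-Meier is of little use with 10 per arm because the median may not be reached. For assumed rescue rates of 30%, 40% and 50% and no dropout, the chance of four or fewer rescues in 10 is 85%, 63% and 38%. If the curve must fall below 50% rather than reach it, the chances are 95%, 83% and 62%. The rates are assumptions, the median is only one summary, and the SAP does not limit the output to it. The curve remains.

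On denominators, the word observed in the endpoint suggests counting subjects seen at the visit, so keeping withdrawn subjects in is a choice and not a correction. On the contingency tables, the SAP does not plan to use post-rescue values. The natural assessment is the one that supported the rescue, and SAP section 12 counts unscheduled assessments as observed data. The visit rule merely leaves the wrong pairing open. Finally, the investigator may withhold rescue, so rescue-free status is not a pure measure of drug effect.

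What remains is that the endpoint is listed separately from time to first rescue and has neither a definition, nor a denominator, nor a table, and that the basis for criteria met is unstated.

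**Conclusion.** The point holds as a gap in definition and reporting, plus a separate misclassification risk in Tables 14.2.4.5 to 14.2.4.8. On the cumulative reading, the by-visit receipt tables leave the endpoint open by up to 50 percentage points at Month 6 (40% to 90%) in the one-per-visit illustration, or 40 points if re-treatment is at most every second visit. Other planned tables narrow or close that range, but none is tied to this endpoint or to visits. The choice of denominator moves the result by about 10 points in the small examples. The size of the pairing problem depends on how many rescues are given at unscheduled visits, which the documents cannot tell us.

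The study is descriptive, with no hypothesis testing, so no error rate, power or sample-size statement is affected. It should be corrected before analysis because the endpoint is a listed secondary one and the repair is small.

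**What to change.** 1. In SAP 12.3, define rescue-free at a visit as no study-eye rescue from Day 1 up to and including that visit. Add number and percent to Tables 14.2.4.1 to 14.2.4.4 from Month 1. Prespecify one denominator that fits the word observed in the endpoint. Show on separate lines the subjects who withdrew after rescue and those who withdrew unrescued, so that a reader can work out the alternative.

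2. Add Kaplan-Meier rescue-free estimates and numbers at risk at the visit days to Tables 14.2.3.1 to 14.2.3.4, as supportive output. Use a visit-based time scale or a final time point that takes in rescues given at the Month 6 visit. Fix in advance which figure leads; it should not depend on whether dropouts occur.

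3. In Tables 14.2.4.5 to 14.2.4.8, classify criteria met for each rescue from the last BCVA and CST on or before the rescue date, unscheduled assessments included. Put rescues without such an assessment on a separate line, since Protocol 6.4 does not require BCVA or OCT at unscheduled visits.

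The cost is SAP wording and a few table rows. Items 1 and 2 use rescue dates that are already collected. Reported durability may look less favourable. No rescue criterion or other clinical rule is changed.

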### 13. Safety Analyses

All safety analyses will be conducted using the SS.

#### 13.1 Adverse Events

An adverse event (AE) is defined as any untoward medical occurrence associated with the use of a drug in humans, whether it is considered drug related. An AE can therefore be any unfavorable and unintended medical diagnosis, sign, or symptom; any new undesirable medical occurrence or unfavorable or unintended change in a pre-existing condition that occurs during or after study treatment; or laboratory abnormality, vital sign, or ophthalmic assessment that is assessed as clinically significant and different from baseline (e.g., requiring discontinuation of study treatment, specific treatment, or a change in subject management). If possible, changes in laboratory results or changes in vital signs that meet the definition of an AE should be reported as a medical diagnosis rather than as the abnormal value. All AEs will be coded using MedDRA Version 22.0.

A treatment-emergent adverse event (TEAE) is an AE with an onset anytime from when the subject has received study drug through 30 days after the study ends whether it is considered causally related to the study drug. Adverse events recorded in the eCRF which began prior to treatment will not be included in the summary tables but will be included in the AE data listings. An SAE is any event that involves or results in any of the following outcomes:

- Death
- Life-threatening occurrence (i.e., if in the view of the investigator or Sponsor, the event's occurrence placed the subject at risk of death at the time of the event; it does not refer to an event which hypothetically might have caused death if it were more severe)
- Requires in-patient hospitalization or prolongation of existing hospitalization (hospitalization for elective surgery for a pre-existing condition or for surgery planned before study entry is not considered an SAE)
- A persistent or significant disability/incapacity (permanent or substantial disruption of the subject's ability to perform normal life functions); this definition is not intended to include experiences of relatively minor or temporary medical significance
- Congenital anomaly/birth defect (an AE that occurs in the child or fetus of a subject exposed to study drug prior to conception or during pregnancy)
- An important medical event or serious medical condition that does not meet any of the above criteria may be considered an SAE if, based upon appropriate medical judgment, it jeopardizes the subject or requires medical or surgical intervention to prevent one of the outcomes listed above. Examples of such medical events include allergic bronchospasm requiring intensive treatment in an emergency room or at home, blood dyscrasias, or convulsions that do not result in in-patient hospitalization, or the development of drug dependency or drug abuse.

An overall summary will be presented that includes the number of TEAEs and the number and percentage of subjects who experienced at least one TEAE, total and by cohort. This summary will also include breakdowns of TEAEs further categorized as ocular (study eye and non-study eye, separately), non-ocular, serious TEAEs, TEAEs by maximum severity, treatment-related TEAEs, and TEAEs leading to subject withdrawal.

Additional summaries of TEAEs will be provided showing the number and percentage of subjects who experienced at least one TEAE and total number of events. These summaries will be presented by SOC and PT. Non-ocular TEAEs will be summarized using discrete summary statistics and presented by cohort and total subjects at the subject and event level by SOC and PT. Ocular TEAEs will be similarly summarized at the subject level for study and non-study eyes separately. If a subject has multiple TEAEs coded to the same PT within same SOC, that PT will only be reported once. As with the PT, if a subject reports multiple conditions within the same SOC, that SOC will only be reported once at the subject level. In the summary, SOCs are listed in order of decreasing frequency for total subjects. PTs are listed in order of decreasing frequency within each SOC for total subjects. The occurrence of non-ocular and ocular TEAEs will also be tabulated by SOC and PT for the following: maximal severity and suspected relationship to study drug.

Separate summaries will be provided for the following categories of AEs:

- Ocular TEAEs in the study eye
- Ocular TEAEs in the non-study eye
- Non-ocular TEAEs
- Treatment-related ocular TEAEs in the study eye
- Treatment-related ocular TEAEs in the non-study eye
- Treatment-related non-ocular TEAEs
- Ocular serious TEAEs in the study eye
- Ocular Serious TEAEs in the non-study eye
- Non-ocular serious TEAEs
- Treatment-related ocular serious TEAEs in the study eye
- Treatment-related ocular serious TEAEs in the non-study eye
- Treatment-related non-ocular TEAEs
- Ocular TEAEs by maximal severity in the study eye
- Ocular TEAEs by maximal severity in the non-study eye
- Non-ocular TEAEs by maximal severity
- TEAEs leading to premature study discontinuation (if applicable)

The NCI-CTCAE (National Cancer Institute – Common Terminology Criteria for Adverse Events) (version 4.03) is a descriptive terminology that will be used to grade the severity of non-ocular AEs reported in this

study. The NCI-CTCAE displays Grades 1 through 5 with unique clinical descriptions of severity for each AE based on this general guideline:

- Grade 1: Mild; asymptomatic or mild symptoms; clinical or diagnostic observation only; intervention not indicated
- Grade 2: Moderate; minimal, local, or noninvasive intervention indicated; limiting age-appropriate instrumental activities of daily living (ADL)\*
- Grade 3: Severe or medically significant but not immediately life-threatening; hospitalization or prolongation of hospitalization indicated; disabling; limited self-care ADL\*\*
- Grade 4: Life-threatening consequences; urgent intervention indicated
- Grade 5: Death related to an AE

A semicolon indicates “or” within the above descriptions. A single dash (–) can be used to indicate that a grade is not available. Not all grades are appropriate for all AEs. Therefore, some AEs are listed with fewer than 5 options for grade selection.

- \* Instrumental ADL refer to preparing meals, shopping for groceries or clothes, using the telephone, managing money, etc.
- \*\* Self-care ADL refer to bathing, dressing and undressing, feeding self, using the toilet, taking medications, and not being bedridden.

The severity grading of ocular AEs reported in this study will not employ the NCI-CTCAE criteria defined above but will be graded as described here. Severity of an ocular AE is defined as a qualitative assessment of the degree of intensity of an AE as determined by the Investigator or reported to him/her by the subject. The assessment of severity is made irrespective of relationship to the study drug or seriousness of the event and should be evaluated according to the following scale:

- *Mild*: Event is noticeable to the subject but is easily tolerated and does not interfere with the subject's daily activities.
- *Moderate*: Event is bothersome, possibly requiring additional therapy, and may interfere with the subject's daily activities.
- *Severe*: Event is intolerable, necessitates additional therapy or alteration of therapy, and interferes with the subject's daily activities.

Summaries of TEAEs by maximal severity will be provided showing the number and percentage of subjects who experienced at least one TEAE and total number of events. These summaries will be presented by SOC and PT. Non-ocular TEAEs will be summarized using discrete summary statistics and presented by cohort and total subjects at the subject and event level by SOC and PT. Ocular TEAEs will be similarly summarized at the subject level for study and non-study eyes separately.

The relationship of each AE to the study drug should be determined by the Investigator using these explanations:

- *Related*: A reasonable possibility exists that the study drug caused the AE.
- *Not Related*: A reasonable possibility does not exist that the study drug caused the AE.

Summaries of all ocular and non-ocular TEAEs, TEAEs by maximal severity, TEAES related to the study drug, and serious TEAEs will also be tabulated by study site for each cohort and total subjects. All ocular AEs occurred in study eye and non-study eye will be summarized separately.

All TEAEs will be presented in a subject listing. The TEAEs leading to study treatment discontinuation will be listed separately. In addition, all serious AEs will be presented in a separate listing.

